2.2 Outcome Measures

The primary outcome measures are safety and anti-cancer activities (assessed based on Response Rate [RR]).

The secondary outcome measures are:

- Progression-Free-Survival (PFS).
- Overall Survival (OS).

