5.1 Pre-Study Screening Tests and Safety Assessment

5.1.1 *Pre-Study Screening Tests*

Pre-study screening tests, which are also enrollment evaluations, must be performed according the following time frames:

Within 4 weeks: tumor assessments based on contrast CT of chest, abdomen, and pelvis, and optional blood and serum samples.

Within 2 weeks: medical history, physical exam, vital signs, height, weight, ECG, ECOG, evaluation of symptoms and medications, clinical chemistry, hematology, coagulation, and troponin I.

Within 1 week: pregnancy test for women of child-bearing potential.

5.1.2 *Safety Assessment*

The safety of CPI-613 will be assessed from the first dose to 1 month after last dose of CPI-613. The assessment will be based on:

- evaluation of symptoms
- vital signs
- ECOG performance status and survival
- clinical chemistry
- renal function
- hematology
- coagulation
- cardiac safety assessments via troponin I and ECG

The specifics of the safety tests are described in Section 5.2. All safety assessment tests are performed during screening (performed within 2 weeks prior to treatment with CPI-613 during Pre-Cycle 1), on Day 5 during Pre-Cycle 1, and prior to each treatment cycle with results available for review within 24 hrs before administration the anti-tumor agents. Chemistries, hematology, and renal function will also be performed on Days 1 and 4 of each treatment week during the first 2 cycles. ECOG performance status and survival will be assessed on Day 1 of each treatment week.

5.1.3 *Tumor Assessment*

Tumor response to treatment will assessed at baseline, and initially after the time frame encompassing the pre-cycle 1 treatment and the first three cycles using

Comprehensive Cancer Center of Wake Forest University
A Pilot Study: Open-Label Clinical Trial of CPI-613 in Patients with Advanced Bile Duct
Cancers
CCCWFU # 59212

contrast CT of the chest, abdomen and pelvis as well as serum levels of tumor marker CA-19-9 and performance status. Should the principal investigator determine that tumor progression has occurred the patient will be removed from the study. Should the principal investigator determine that the patient has stable disease or has had a favorable response, those patients will continue treatment with CPI-613 for an additional three cycles (approximately three months). At that time, patients will then undergo re-imaging contrast CT, CA-19-9 and performance status.

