According to the Response Evaluation Criteria in Solid Tumors (RECIST), the efficacy of treatment for solid tumors is determined by the tumor size. RECIST criteria are the golden standard to evaluate the tumor. In this study RECIST criteria will be used to evaluate response. However, there is a *pseudoprogression* phenomenon described with the use of CPI-613 in Phase I solid tumor studies (Lee et al. 2012).

It is felt that if CPI-613-induces necrosis of the tumor lesion there may be some radiographic evidence for increasing size. CPI-613 induces tumor necrosis due to its mechanism of action – selectively targeting the altered form of mitochondrial energy metabolism in tumor cells, causing changes in mitochondrial enzyme activities and redox status, which leads to apoptosis, necrosis, and autophagy of tumor cells (2,3,7,17,18).

For the purposes of this study, pseudoprogression will be defined and considered in patients who meet RECIST criteria of progression. It will be the treating physician's discretion to continue treatment in this situation if the patient is deemed to be getting clinical palliative benefit. In these patients, the study drug can be given for another two cycles prior to making definitive determination of progression or response.

Assessment of tumor response will be the responsibility of the principal investigator and should be based on radiologic findings (i.e., contrast CT of the chest, abdomen, and pelvis, and MRI of the abdomen), CA-19-9 and performance status.

OS will be monitored bimonthly via telephone contact after treatment termination. (**Note:** During the bimonthly post-study telephone contact, information related to cancer treatment received after the study will also be collected). OS and PFS will be calculated from the first day of treatment. The duration of OS will be measured until the date of death or censored at follow-up. The duration of response (evaluated by PFS) will be measured from the date a first objective response is documented until the first sign of progression assessed by MRI and CT.

****NOTE:** Tumor necrosis alone should not be criteria for determining

Comprehensive Cancer Center of Wake Forest University
A Pilot Study: Open-Label Clinical Trial of CPI-613 in Patients with Advanced Bile Duct
Cancers
CCCWFU # 59212

progression.

Safety and RR of CPI-613 are the primary endpoints, whereas PFS and OS are secondary endpoints.

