Pseudoprogession will be ruled out by allowing patients to receive the study drug for another 2 cycles after the first response assessment before making definitive assessment of progression or response. However, patients will not be allowed to continue treatment with CPI-613 at the time of “pseudo-progression” if any of the following criteria are met:

- a. The patient does not meet eligibility criteria set at the start of the protocol.
- b. Biliary function worsens.
- c. The patient has symptomatic progression.

OS will be determined from the first dose of CPI-613 to death, assessed up to 3 years after the first dose of CPI-613. Post-study survival, medical and cancer treatment information will be collected bimonthly via telephone contact after treatment termination.

RR is defined as % of patients who experienced a Complete Response (CR) or Partial Response (PR). CR and PR are based on Response Evaluation Criteria in Solid Tumor (RECIST) Version 1.1 Eisenhauer et al. 2009). The best response recorded from the start of the treatment until Disease Progression (DP) will be considered.

PFS will be determined from the first dose of CPI-613 to DP or death due to any cause, assessed up to 3 years after the first dose of CPI-613.

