Appendix D – Efficacy Assessment Form

ORIS PID: _____

Date Completed: ____ / ____ / ____

Visit Type: Pre-Study Cycle 1 Visit Cycle 2 Visit Cycle 3 Visit Cycle 4 Visit
 Cycle 5 Visit Cycle 6 Visit Cycle 7 Visit Cycle 8 Visit Cycle 9 Visit
 Cycle 10 Visit Cycle 11 Visit Cycle 12 Visit
 Other (Specify: _____)

ECOG Performance Status (Date Performed: ____ / ____ / ____):

- 0 Fully active, able to carry on all pre-disease performance without restriction.
- 1 Restricted in physically strenuous activity but ambulatory and able to carry out work of a light or sedentary nature, e.g., light house work, office work.
- 2 Ambulatory and capable of all self-care but unable to carry out any work activities. Up and about more than 50% of waking hours.
- 3 Capable of only limited self-care. Confined to bed or chair more than 50% of waking hours.
- 4 Completely disabled. Cannot carry on any self-care. Totally confined to bed or chair.

Date of CT (Chest/abdomen/pelvis): ____ / ____ / ____

CT (Chest/abdomen/pelvis) Result:

- Stable disease
- Mixed response
- Pseudo-progression (for 1st CT only)
- Partial response
- Progression of disease

Were new lesions identified on CT (Chest/abdomen/pelvis)? Yes No

Were the new lesions confirmed by biopsy? Yes No NA

Has this subject progressed? (As determined by the Principal Investigator) Yes No

Was tissue obtained for research purposes? Yes No

COMMENTS: _____

Comprehensive Cancer Center of Wake Forest University
A Pilot Study: Open-Label Clinical Trial of CPI-613 in Patients with Advanced Bile Duct
Cancers
CCCWFU # 59212

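### Section 5.1.3 gives two conflicting bases for the primary response endpoint, RECIST 1.1 alone or imaging plus CA-19-9 and performance status, and does not say which prevails

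*Combined protocol and SAP*

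**What the plan says.** Section 2.2 makes response rate (RR) a primary outcome alongside safety. Section 5.1.3 defines RR as the percentage of patients with a complete response (CR) or partial response (PR), and says "CR and PR are based on Response Evaluation Criteria in Solid Tumor (RECIST) Version 1.1". It also states "In this study RECIST criteria will be used to evaluate response".

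The same section gives a second basis. On who makes the call and from what, it says "Assessment of tumor response will be the responsibility of the principal investigator and should be based on radiologic findings". The sentence does not stop there: after naming CT it continues "and MRI of the abdomen), CA-19-9 and performance status". The opening paragraph of 5.1.3 likewise has tumor response assessed using "contrast CT of the chest, abdomen and pelvis as well as serum levels of tumor marker CA-19-9 and performance status", and then says "Should the principal investigator determine that tumor progression has occurred the patient will be removed from the study".

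Elsewhere, progression is tied to imaging. Section 1 and the pseudo-progression text in 5.1.3 speak of progression by RECIST, and 5.1.3 ends the duration of response at progression seen on MRI and CT.

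The Appendix D form has a CT result item (stable disease, mixed response, pseudo-progression for the first CT only, partial response, progression), a question on new lesions, and a separate item: "Has this subject progressed? (As determined by the Principal Investigator". Section 9.0 will report the proportions with CR, PR, SD and PD, and the RR with a 95% confidence interval. It names no response criteria.

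**The concern.** A RECIST 1.1 response is an imaging category. A response call that also draws on a serum marker and performance status is a different quantity, even if it usually gives the same answer. The plan labels the endpoint as the first and instructs the assessor to produce the second.

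The trial is open-label and single-arm, and the principal investigator makes the call. Where the inputs disagree, the category depends on how one unblinded person weighs them. Section 9.0 intends the results to inform likely effect sizes, so a rate reported as RECIST but partly resting on other information could be carried into later planning under the wrong label.

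**Working it through.** The check is mainly textual, with a short calculation for scale.

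**1. The two bases for response, side by side (all in 5.1.3).**

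| Place | Basis for the call |
|---|---|
| Definition of RR | RECIST 1.1 |
| General statement on response criteria | RECIST |
| Sentence on the investigator's responsibility | CT, MRI, CA-19-9, performance status |
| Opening paragraph on scheduled assessment | CT, CA-19-9, performance status |

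The last two rows are about assessing tumor response. They are not limited to decisions on continuing treatment.

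**2. Is there a rule for disagreement?** Take a patient whose lesions shrink but fall short of PR, while CA-19-9 falls and performance status improves. The RR definition gives SD; the responsibility sentence leaves the category open. Now take a patient whose lesions meet PR while CA-19-9 rises or performance status worsens. The definition gives PR; the other sentence again leaves it open. No threshold for either measure, weighting or order of precedence appears anywhere. The disagreement can run in either direction.

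**3. Progression.** Section 1 and parts of 5.1.3 point to RECIST and to MRI and CT. Against that, the opening paragraph of 5.1.3 leaves the determination to the investigator directly after an assessment that includes CA-19-9 and performance status, and the Appendix D item names no criteria. The criteria are left open rather than plainly contradicted.

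**4. Link to RR.** Under 5.1.3 the best response counts only up to progression. A later progression call lengthens the window in which a response can count, as well as PFS.

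**5. Does the form settle it?** In part. The CT result is recorded apart from the investigator's progression item. But it has no CR option, although CR is a component of RR and a category in Section 9.0. It has no field for lesion sums. The text does not say whether the CT category or the investigator's item enters RR and PFS.

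**6. Scale.** Section 9.0 has 10 patients in the analytic sample and says the two-sided 95% interval extends no more than 0.31 from the observed rate. This reproduces with the normal approximation at p = 0.5: 1.96 × √(0.5 × 0.5 / 10) = 0.3099. One reclassified patient moves RR by 1/10 = 0.10, about a third of that distance (0.10 / 0.31 = 0.32).

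| Responders | RR | Exact 95% interval |
|---|---|---|
| 1 of 10 | 0.10 | 0.003 to 0.445 |
| 2 of 10 | 0.20 | 0.025 to 0.556 |

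The exact intervals extend further than 0.31 (for 2 of 10, 0.556 − 0.20 = 0.356). The plan does not name its interval method, and nothing in this point depends on it.

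**The case against.** The strongest defence is that the specific definition governs. RR is defined by RECIST 1.1, RECIST is named again as the means of evaluating response, and no CA-19-9 or performance-status threshold is given for any category. On that reading, the broader sentence only lists what the investigator reviews at restaging. It is a reasonable guess at the intent, but the documents do not say so. The broader sentence is about the assessment of tumor response, it is addressed to the person who assigns the category, and nothing subordinates it to the definition. The lack of a threshold leaves the role of the two measures undefined; it does not remove them.

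Two parts of the defence stand. First, a reader might infer that Appendix D records only the investigator's overall judgement. It does not: ECOG status, the CT result and the progression item are separate, and the only response category on the form is labelled as a CT result. The form also does not show that lesion measurements go unrecorded elsewhere; eligibility requires measurable disease by RECIST 1.1, with source documentation. Second, a reader might infer that progression is as openly in conflict as response. The references to RECIST progression and to MRI and CT make that too strong.

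It can also be said that this is a descriptive pilot with no test and no decision threshold on RR, and that one patient in 10 is 10 points for any misclassification. Both are true. They limit the consequence, but a primary endpoint still needs one definition.

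**Conclusion.** The conflict is real and concerns a primary endpoint. Section 5.1.3 bases response on RECIST 1.1 in one place and on imaging, CA-19-9 and performance status in another, with no order of precedence. For progression, the documents leave the criteria open rather than contradicting themselves outright; this matters because progression closes the window for best response and determines PFS.

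A reader might go further and infer that responses will be upgraded or progression deferred. The documents do not support that. They allow disagreement in either direction and give no information on how often it would arise, so neither the size nor the direction of any bias can be derived. What can be said is that each reclassified patient moves RR by 10 percentage points, given the 10-patient analytic sample in Section 9.0. The conclusion assumes that the sentences in 5.1.3 mean what they say about assessing tumor response. If CA-19-9 and performance status were meant only as background for the investigator, one sentence would settle the matter.

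**What to change.** Reconcile the paragraphs of Section 5.1.3 with each other, with Section 9.0 and with Appendix D:

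- In 5.1.3 and 9.0, state that CR, PR, SD and PD for RR, and progression for PFS, are assigned by RECIST 1.1 criteria alone, covering target, non-target and new lesions. A wording restricted to lesion measurements would be too narrow, because it could leave out the new lesions that Appendix D records.
- State that CA-19-9 and performance status are reported separately as supportive information.
- In Appendix D, add a CR option and the target-lesion sum, and say which item supplies the category used for RR and PFS.

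Make no change to the rules on continuing or stopping treatment. The pseudo-progression text, which postpones the definitive call in some patients, raises a separate question of timing; the new sentence should make clear which scan dates progression for the endpoint.

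The cost is a few sentences and a small form revision, with no extra scans, readers or patients. The price for the study team is that RR may come out slightly less favourable if any call would otherwise have been raised by the marker or performance status.

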Table 5-2 (below) provides an overview of the study procedures for all treatment cycles and the follow-up period. The specifics are described in subsequent sections.

Table 5-2: Study Procedures for All Treatment Cycles and Follow-Up Period

Assessments	Cycles 1 and 2 (Each cycle is 4 weeks)								Cycles 3 through 12 (Each cycle is 4 weeks)								Follow-Up Every 2 months until death
	Week 1		Week 2		Week 3		Week 4		Week 1		Week 2		Week 3		Week 4		
	D1	D4	D1	D4	D1	D4	D3,4,or 5		D1	D4	D1	D4	D1	D4	D3, 4, or 5		
CPI-613 ¹	√	√	√	√	√	√			√	√	√	√	√	√			
Evaluation of symptoms and vital signs	√ ²		√ ²		√ ²				√ ²		√ ²		√ ²				
ECOG performance status and survival	√ ²		√ ²		√ ²				√ ²		√ ²		√ ²				
Clinical chemistry, hematology ^{2,3,9}	√ ²	√	√	√	√	√			√ ²								
Cardiac: Troponin I and ECG ⁹	√ ²								√ ²								
CT w/ contrast (chest/abdomen/pelvis)																√ ⁴	
CA-19-9																√ ⁴	
Plasma CPI-613 concentrations, possibly metabolite concentrations, and possibly other analyses ⁶	√ ⁸																
Optional blood and serum samples ¹⁰																√ ⁴	
Phone contact																√ ⁷	

ECOG = Eastern Cooperative Oncology Group; hr = hour; min = minute; D1 = day 1; D4 = day 4.

¹ CPI-613 is given as a 2-hr IV infusion via a central venous catheter. Treatment with CPI-613 may be adjusted +/- 1 day.

² These tests are performed with results available for review within 24 hrs before administration of the anti-tumor agents.

³ Specific chemistries are listed in section 5.2.2. Renal function will be assessed utilizing the Cockcroft-Gault formula.

⁴ Performed at the following time points: during week 4 (preferably Wednesday or later) of cycle 3 for all patients. For patients without progression, perform during week 4 of cycles 6, 9, and 12. In patients where progression was detected from the cycle 3 scan, perform during week 4 of cycle 5. If patient remains on study after cycle 5, perform every 3 months thereafter.

⁶ Plasma samples will be obtained pre-dose (~5 min before dosing), and at 0.5, 1, 1.5, 2, and 4 hrs post-dose of CPI-613.

⁷ Survival and post-study cancer treatment will be monitored bimonthly via telephone contact after the patients are taken off the trial.

⁸ Cycle 1 only

⁹ Within 1 week: pre-study labs and ECG obtained before enrollment may be used for Day 1

¹⁰ Optional blood and serum samples are for possible testing of biomarkers, predictors of biological responses, toxicity, genotype vs. drug response relationship, etc.

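### The primary response rate has no stated confirmation rule for CR or PR, while a first progression may get a second CT, so the rate is at risk of upward bias in a 10-patient single-arm trial.

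*Combined protocol and SAP*

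**What the plan says.** **Response.** RR is a primary outcome (Section 2.2). Section 5.1.3 defines it as the percentage of patients with CR or PR and adds that "CR and PR are based on Response Evaluation Criteria in Solid Tumor (RECIST) Version 1.1". It then sets the scoring rule: "The best response recorded from the start of the treatment until Disease Progression (DP) will be considered". Duration of response is "measured from the date a first objective response is documented until the first sign of progression". No second assessment or minimum interval is mentioned there or in Section 9.0, and the Appendix D form has no field for one. The principal investigator is responsible for the judgement, in an open-label trial, using imaging, CA-19-9 and performance status.

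**Progression.** Section 5.1.3 allows "another 2 cycles after the first response assessment before making definitive assessment of progression or response". Table 5-2, footnote 4, schedules the scan: "In patients where progression was detected from the cycle 3 scan, perform during week 4 of cycle 5". Three conditions bar the extra cycles (eligibility no longer met, worse biliary function, symptomatic progression). Continuing is at the treating physician's discretion, and Appendix D offers the pseudo-progression box for the first CT only.

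**Scan schedule.** All patients have a CT in week 4 of cycle 3. After that: "For patients without progression, perform during week 4 of cycles 6, 9, and 12".

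**Analysis.** Section 9.0 analyses 10 patients descriptively, with a 95% interval for RR.

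**The concern.** A second look is written out for an unfavourable reading and none for a favourable one. Where the progression re-scan is used, a reading against the drug can be overturned. As the text stands, a reading in its favour is counted once recorded and stays counted. Taking the best of several readings also gives more chances for a false PR as scans accumulate.

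There is no control arm in which the same error would appear, and the reader knows the treatment. Section 9.0 intends these data to indicate likely effect sizes, so an inflated rate would carry into the planning of later work.

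There is a second gap. Section 5.1.3 defers the definitive call for either progression or response, but counts responses only until DP. A patient with RECIST progression at cycle 3 and a PR at cycle 5 is a responder if DP was deferred, and a non-responder if DP occurred at cycle 3. The text does not settle which.

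**Working it through.** **1. The plan's own figure.** Section 9.0 says the 95% interval for RR will extend at most 0.31 from the estimate. The Wald half-width at its maximum is 1.96 × √(0.5 × 0.5 / 10) = 0.3099, so 0.31 reproduces. This point does not change it. (The interval method is not named; the exact interval reaches 0.356 from the estimate at 2/10.)

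**2. Direction on the same scans.** Every confirmed responder has at least one scan read as CR or PR, so confirmed responders are a subset of unconfirmed ones. Hence unconfirmed RR ≥ confirmed RR, with no assumption about error rates.

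**3. Effect of one patient.** With n = 10, one reclassified patient moves RR by 1/10 = 10 points. Exact 95% intervals: 0/10 gives 0-30.8%, 1/10 gives 0.3-44.5%. The same shift applies to one patient with progression at cycle 3 and PR at cycle 5.

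**4. Illustrative size.** Assume a probability f that one scan of a non-responder is misread as PR. The documents give no value; 2% and 5% are used. Let k be the number of scans (cycles 3, 6, 9 and 12, so at most 4 in 12 cycles). With independent errors:

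- at least one false PR: 1 − (1 − f)^k
- two consecutive false PRs: f² for k = 2; for k = 4, 1 − [(1 − f)⁴ + 4f(1 − f)³ + 3f²(1 − f)²]

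| k | Single scan counts, f = 2% / 5% | Two consecutive needed, f = 2% / 5% |
|---|---|---|
| 1 | 2.0% / 5.0% | none can be confirmed |
| 2 | 4.0% / 9.8% | 0.04% / 0.25% |
| 4 | 7.8% / 18.6% | 0.12% / 0.7% |

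For 10 patients with no true responders and two scans each, the chance of at least one false responder is 1 − 0.98²⁰ = 33% or 1 − 0.95²⁰ = 64% unconfirmed. With confirmation it is 1 − (1 − 0.0004)¹⁰ = 0.4% or 1 − (1 − 0.0025)¹⁰ = 2.5%.

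**5. How many scans are realistic.** Counting the pre-cycle week, the CTs fall at about weeks 1 + 12 = 13, 1 + 24 = 25 and, for cycle 12, 1 + 48 = 49. Section 1 gives overall survival of about 6 months. One or two scans is therefore the likelier case for a non-responder, and four is an upper end.

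**6. Correlated errors.** If a misreading persists because reader, lesions and baseline are the same, then at full correlation the risk stays at f (2-5%) for any k, confirmed or not. The confirmed column above is a best case.

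**7. Bias against the true rate.** With true rate π and per-scan sensitivity s, expected unconfirmed RR = π[1 − (1 − s)^k] + (1 − π)[1 − (1 − f)^k].

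- π = 10%, s = 90%, k = 2: f = 2% gives 0.0990 + 0.0356 = 13.5% (+3.5 points); f = 5% gives 0.0990 + 0.0878 = 18.7% (+8.7 points).
- π = 20%, s = 80%, k = 1, f = 2%: 0.160 + 0.016 = 17.6% (−2.4 points).

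The confirmed rate has its own error. For π = 10%, s = 90%, k = 2, f = 2% it is 0.10 × 0.81 + 0.90 × 0.0004 = 8.1% (−1.9 points).

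**The case against.** A reader might infer that the protocol makes one scan sufficient by rule. It does not say so. RECIST 1.1 is adopted by reference, and whether its confirmation provisions apply cannot be checked from these documents. What stands is that no confirmation step is stated, and that the best-response and duration wording reads most naturally without one.

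A reader might also infer that the trial itself says CTs mislead in the drug's favour. The documents describe only the opposite error, in which inflammation and necrosis look like growth. They offer no mechanism for false shrinkage, so false PRs here are an assumption about ordinary reading error by an unblinded assessor.

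Nor does every first progression get a second scan. The allowance is discretionary, conditional and limited to the first CT, and other text contradicts it. Progression first seen at cycle 6, 9 or 12 has no stated second look. The imbalance is real only where the re-scan is used.

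It is also fair to say that response does not rest on CT alone, that patients with a favourable response are re-imaged after three more cycles, and that this is a small descriptive pilot in which 10 points lies within the stated precision. These limit the consequence. They do not settle how a response that is gone at the next CT is counted, and a wide interval does not remove a shift in its centre.

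Finally, requiring persistence for about three months in a population with survival near 6 months turns RR into something closer to a durable-response rate. That is a sound reason not to make the confirmed rate the only headline.

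**Conclusion.** The point holds as a risk of upward bias, not as a demonstrated bias. Two parts need no assumption: unconfirmed RR cannot be below confirmed RR on the same scans, and one spurious PR in 10 moves RR by 10 points. The size is not derivable from the documents. The 2-5%, 4-10% and 8-19% figures for one, two and four scans rest on an assumed 2-5% false-PR rate and independent errors, and confirmation would remove less if errors are correlated. Against the true rate, upward bias is the usual result in the scenarios tried, but one-scan cases with imperfect sensitivity can go the other way (−2.4 points in the example). The status of a cycle 5 PR after cycle 3 progression is an open definition, whatever the error rate.

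**What to change.** In Sections 5.1.3 and 9.0:

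- Define a confirmed response as CR or PR still present at the next scheduled CT.
- Report confirmed RR and single-scan best-response RR side by side, each with a 95% CI by a named method. Rest any statement about activity on both rates, not on the unconfirmed rate alone.
- Show responses with no later CT as unconfirmed, including those first seen at cycle 12, after which Table 5-2 lists no CT for non-progressing patients.
- State whether a PR at cycle 5 after RECIST progression at cycle 3 counts as a response before DP.
- Add a confirmation field to Appendix D.

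The texts on handling a first progression must also be reconciled. Sections 1 and 5.1.3, Table 5-2 footnote 4 and Appendix E describe two further cycles or a cycle 5 CT; another paragraph of 5.1.3 removes the patient once progression is determined; Section 6.3 refers to one additional cycle.

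The cost is a few sentences, one table row and one form field. Responses first seen at cycle 3, 6 or 9 can be confirmed on CTs already scheduled. The drawback is that the confirmed rate may be lower, partly because some patients will stop before the next CT about three months later. Showing both rates keeps that visible.
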